Other secondary objectives	
Other efficacy secondary objectives	Other efficacy secondary endpoints
To compare efficacy of plitidepsin 1.5 mg or 2.5 mg versus the control in terms of hospital readmission related to COVID-19.	Percentage of patients in each study group who require hospital readmission related to COVID-19 through Day 31.
To compare efficacy of plitidepsin 1.5 mg or 2.5 mg versus the control in terms of clinical evolution.	Percentage of patients in each study group and in each of the categories of the 11-point WHO Clinical Progression Scale on Days 4, 8, 15 and 31 (See Appendix 13 - World Health Organization (WHO) Clinical Progression Scale).
To compare efficacy of plitidepsin 1.5 mg or 2.5 mg versus the control in terms of the need of supplementary oxygen.	Percentage of patients in each study group requiring oxygen therapy on Days 4, 8, 15 and 31.
To compare efficacy of plitidepsin 1.5 mg or 2.5 mg versus the control in terms of the need of intensification of respiratory or intensive care support.	Time to intensification of respiratory support (WHO >6 [intubation]) (See Appendix 13 - World Health Organization (WHO) Clinical Progression Scale).
	Total duration of intensive care unit (ICU) stay for each study group.
	Percentage of patients in each study group requiring high-flow oxygen on Days 4, 8, 15, and 31.
	Percentage of patients in each study group requiring non-invasive mechanical ventilation on Days 4, 8, 15 and 31.

	Percentage of patient in each study group requiring invasive mechanical ventilation or ECMO on Days 4, 8, 15, and 31.
To compare efficacy of plitidepsin 1.5 mg or 2.5 mg versus the control in terms of the need of intensification of pharmacological therapies.	
Time to initiation with immune-modulating drugs.
 
Time to initiation with antiviral drugs.
 
Percentage of patients receiving subsequent immune-modulating drugs on Days 4, 8, 15 and 31.
 
Percentage of patients receiving subsequent antiviral drugs on Days 4, 8, 15 and 31.

To compare efficacy of plitidepsin 1.5 mg or 2.5 mg versus the control in terms of superinfections.	Percentage of patients in each study group with nosocomial infection by Days 4, 8, 15 and 31.
To compare efficacy of plitidepsin 1.5 mg or 2.5 mg versus the control in terms of mortality.	Mortality in each study group on Days 4, 8, 15 and 31.

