2. OBJECTIVES AND ENDPOINTS

2.1. Objectives

Primary objective

- To compare efficacy of plitidepsin 1.5 mg or 2.5 mg *versus* the control assessing the need of supplementary oxygen.

Key secondary objective

- To compare efficacy of plitidepsin 1.5 mg or 2.5 mg *versus* the control assessing the time to sustained hospital discharge.

Secondary Objectives

- To compare efficacy of plitidepsin 1.5 and 2.5 mg *versus* control:
 - Assessing clinical status by the 11-category WHO Clinical Progression Scale⁴⁵ (See [Appendix 13 - World Health Organization \(WHO\) Clinical Progression Scale](#)).
 - In terms of the need of advanced oxygen support.
 - In terms of need for intensive care support.
- To compare safety/tolerability of plitidepsin 1.5 mg or 2.5 mg *versus* the control in terms of:
 - adverse events, adverse reactions and mortality.
 - abnormal laboratory parameters.
 - variations of vital signs.
 - ECG variations.

Other secondary objectives

- To compare efficacy of plitidepsin 1.5 mg or 2.5 mg *versus* the control in terms of:
 - hospital readmission related to COVID-19.
 - clinical evolution.
 - the need of supplementary oxygen.
 - the need of intensification of respiratory or intensive care support.
 - the need of intensification of pharmacological therapies.
 - superinfections.
 - mortality.
 - the evolution of viral load.
 - the evolution of inflammatory markers.
 - the immune response against SARS-CoV-2.
- To compare efficacy in the primary endpoint and describe safety/tolerability of pooled plitidepsin arms *versus* control.
- To compare efficacy in the primary endpoint and describe safety/tolerability between plitidepsin arms (1.5 *versus* 2.5 mg) in case both are significantly superior to the control.

- To explore the influence of risk factors or scores for clinical deterioration that were not individually included.
- To compare the results obtained before and after the change of the primary and secondary endpoint (protocol v.6 *versus* v.7).

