2.2. Endpoints

Primary efficacy endpoint

- Time to sustained withdrawal of supplementary oxygen (11-category WHO Clinical Progression Scale ≤ 4) with no subsequent reutilisation during remaining study period (See [Appendix 13 - World Health Organization \(WHO\) Clinical Progression Scale](#)).

Key secondary efficacy endpoint

- Time to sustained (i.e., with no subsequent readmission to Day 31) hospital discharge (since randomisation).

Secondary endpoints

Efficacy:

- Clinical status, as assessed by the 11 category WHO Clinical Progression Scale, at Day 8 (± 1) (See [Appendix 13 - World Health Organization \(WHO\) Clinical Progression Scale](#)).
- Total duration of advanced oxygen support (high-flow nasal oxygen, extracorporeal membrane oxygenation -ECMO-, non-invasive ventilation or mechanical ventilation).
- Percentage of patients in each study group requiring admission to ICU on Days 4, 8, 15, and 31.

Safety/tolerability:

- Frequency of TEAEs;
- Frequency of TEAEs of ≥ 3 according to NCI-CTCAE v5.0;
- Frequency of treatment-emergent adverse events of special interest (AESIs);
- Frequency of serious adverse events (SAEs);
- Frequency of drug-related serious adverse events (i.e., SARs);
- Frequency of adverse events leading to treatment discontinuation;
- Frequency of deaths;
- Change respect to baseline in individual study-defined laboratory parameters (See [Section 7.2.4.](#));
- Change respect to baseline in individual vital signs (See [Section 7.2.5.](#));
- Change respect to baseline in individual study-defined ECG parameters (See [Section 7.2.5.](#)).

Other secondary endpoints

- Percentage of patients in each study group requiring hospital readmission due to COVID-19-related signs or symptoms through Day 31.

- Percentage of patients in each study group and in each of the categories of the 11-category WHO Clinical Progression Scale on Days 4, 8, 15 and 31 (See [Appendix 13 - World Health Organization \(WHO\) Clinical Progression Scale](#)).
- Percentage of patients in each study group requiring oxygen therapy on Days 4, 8, 15 and 31.
- Time to intensification of respiratory support (WHO >6 [intubation]) (See [Appendix 13 - World Health Organization \(WHO\) Clinical Progression Scale](#)).
- Total duration of intensive care unit (UCI) stay for each study group.
- Percentage of patients in each study group requiring high-flow oxygen on Days 4, 8, 15, and 31.

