- Percentage of patients in each study group requiring non-invasive mechanical ventilation on Days 4, 8, 15, and 31.
- Percentage of patients requiring either extracorporeal membrane oxygenation ECMO or invasive mechanical ventilation by Days 4, 8, 15, and 31.
- Time to initiation with immune-modulating drugs.
- Time to initiation with antiviral drugs.
- Percentage of patients receiving subsequent immune-modulating drugs on Days 4, 8, 15 and 31.
- Percentage of patients receiving subsequent antiviral drugs on Days 4, 8, 15 and 31.
- Percentage of patients in each study group with nosocomial infection by Days 4, 8, 15 and 31.
- Mortality in each study group on Days 4, 8, 15 and 31.
- Change in SARS-CoV-2 viral load in each study group from Day 1 before administration of the study drug until Day 8.
- Percentage of patients in each study group with undetectable SARS-CoV-2 viral load on Day 8.
- Change in inflammatory biomarkers (C-reactive protein [CRP], ferritin, interleukin [IL]-6, IL-1 β , IL-10 and tumour necrosis factor alpha [TNF α]) in each study group from baseline until Days 2, 3, 4, 8, and 31.
- Change respect to baseline in individual serological assessments.
- Obesity, hypertension, age and individual co-morbidities included in the Charlson Index ([Appendix 11- Age-adjusted Charlson Index](#)), ISARIC-4C score ([Appendix 14 - ISARIC 4C Mortality & 4C Deterioration Scores](#)), or vaccination status.
- Time to sustained withdrawal of supplementary oxygen (11-category WHO Clinical Progression Scale \leq 4) with no subsequent reutilisation during remaining study period, before (protocol v.6) and after the amendment (protocol v.7).
- Time to sustained (i.e., with no subsequent readmission to Day 31) hospital discharge (since randomisation), before (protocol v.6) and after the amendment (protocol v.7).

Additionally, a dedicated QTc substudy will be performed in a subset of approximately 50 patients with ECGs collected over Days 1 to 3 using Holter monitors to assess treatment impact on QTc prolongation. See [Appendix 8](#) for objectives and respective endpoints planned for the QTc substudy. The substudy patients will have blood sampling for pharmacokinetic assessments over Days 1 to 4.

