7.1.4. Other Efficacy Assessments

The study day (from Day 1 to Day 31 (± 3 days)) on which the following events occurred will be recorded:

- Initiation of supplemental oxygen (of any type)
- Discontinuation of supplemental oxygen (of any type)
- Initiation of respiratory support
- Discontinuation of respiratory support
- Initiation of antivirals or immune-modulating drugs
- Discontinuation of antivirals or immune-modulating drugs
- ICU admission
- ICU discharge
- Hospital re-admission for COVID-19 signs or symptoms
- Hospital discharge
- Death

Additionally, the following information will be gathered for each patient on Days 4, 8 (± 1 day), 15 (± 1 day), and 31 (± 3 days) (yes/no):

- Receiving supplementary oxygen therapy
- Receiving high-flow oxygen
- Receiving non-invasive mechanical ventilation
- Receiving invasive mechanical ventilation or ECMO
- Requiring hospital admission related to COVID-19
- Requiring ICU admission
- Receiving subsequent antiviral therapies or immunomodulatory drugs

- Nosocomial infection
- Death

Based on these data, secondary endpoints for percentages of patients requiring oxygen therapy or different types of ventilation will be calculated and the time (in days) to sustained hospital discharge or withdrawal of supplemental oxygen therapy, percentages of patients with nosocomial infection or receiving subsequent antiviral or immunomodulatory therapies, hospitalisation in ICU, and hospitalisation will be measured.

Laboratory-based efficacy assessments that are to be performed during the study include:

- Proinflammatory biomarkers: (CRP, LDH, ferritin, IL-1 β , IL-6, IL-10, and TNF α) in each study arm from baseline (Day 1 prior to start of the study treatment) to Days 2, 3, 4, 8 (± 1 day), and 31 (± 3 days).
- Serological test (IgG) on Days 1 and 31 (± 3 days).

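### Death cuts short the durations of advanced oxygen support and ICU stay, and the ICU, high-flow and NIV percentages read as status on four fixed days

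*Protocol*

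**What the plan says.** Section 2.1 lists among the secondary objectives a comparison "In terms of the need of advanced oxygen support" and one in terms of intensive care. At that tier Section 2.2 gives each a single endpoint:

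- Advanced oxygen: "Total duration of advanced oxygen support (high-flow nasal oxygen, extracorporeal membrane oxygenation -ECMO-, non-invasive ventilation or mechanical ventilation").
- Intensive care: "Percentage of patients in each study group requiring admission to ICU on Days 4, 8, 15, and 31".

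The lower tier in Section 2.2 adds a second duration, "Total duration of intensive care unit (UCI) stay for each study group". For high-flow oxygen it has "Percentage of patients in each study group requiring high-flow oxygen on Days 4, 8, 15, and 31", and there is a like percentage for non-invasive ventilation on the same four days. Invasive ventilation or ECMO appears in two forms. The synopsis has patients "requiring invasive mechanical ventilation or ECMO on Days 4, 8, 15, and 31"; Section 2.2 has patients "requiring either extracorporeal membrane oxygenation ECMO or invasive mechanical ventilation by Days 4, 8, 15, and 31".

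Section 7.1.4 collects two sets of data. The first is the study day of events: starting and stopping respiratory support, ICU admission and discharge, and death. The second is a yes/no status on Days 4, 8, 15 and 31. It then says that, from the data, "secondary endpoints for percentages of patients requiring oxygen therapy or different types of ventilation will be calculated". Section 8.5.3 limits group comparisons of binary endpoints to Day 8 (±1 day); the other days are descriptive.

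**The concern.** A patient who dies stops accruing days on support. After 5 ventilated days followed by death the raw total is 5; after 14 ventilated days followed by recovery it is 14. On a measure where fewer days means less need, the death scores better. The protocol makes raw duration the only endpoint at its tier for advanced oxygen, and nothing in the endpoint text offsets this.

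The percentages raise a separate question. If they are status on the named day, a patient in ICU from Day 9 to Day 14 counts as not needing ICU on both Day 8 and Day 15. The between-arm comparison then rests on Day 8 alone.

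The stake is two of the three first-tier secondary efficacy objectives. Their results could be hard to interpret, or could favour an arm for the wrong reason.

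**Working it through.** The protocol states no figure that can be reproduced here, so the check is arithmetic on assumed inputs plus a reading of the pilot data in Table 3.

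**1. Effect of death on a raw duration.** Assumptions, not in the protocol: a fraction *p* of an arm needs support, survivors use 10 days, and a fraction *d* of users die after *L* days of support. Then:

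- mean days among users = 10(1 − d) + L·d
- mean over the arm = p × that value
- days free of support to Day 31 among users, death = 0: (1 − d)(31 − 10) = 21(1 − d)

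With L = 3 and p = 14% (close to the pilot's 6/44):

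| d | Days among users | Arm mean | Free days among users |
|---|---|---|---|
| 0% | 10.0 | 1.40 | 21.0 |
| 20% | 8.6 | 1.20 | 16.8 |
| 50% | 6.5 | 0.91 | 10.5 |

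With p = 10% the arm mean falls from 1.00 to 0.65 as d goes from 0% to 50%; with p = 18% it falls from 1.80 to 1.17. Raw duration improves as deaths rise, while days alive and free of support worsen.

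The direction depends on L. At d = 50%:

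- L = 3: 0.5 × 10 + 0.5 × 3 = 6.5
- L = 10: 0.5 × 10 + 0.5 × 10 = 10.0, no effect
- L = 15: 0.5 × 10 + 0.5 × 15 = 12.5, reversed

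A second assumed set has 18% needing support, survivors using 14 days, those who die using 7, and deaths among users of 25% in one arm and 50% in the other. Raw means are 0.18 × (0.75 × 14 + 0.25 × 7) = 2.21 and 0.18 × (0.5 × 14 + 0.5 × 7) = 1.89 days. Days alive and free of support are 0.82 × 31 + 0.18 × 0.75 × 17 = 27.7 and 0.82 × 31 + 0.18 × 0.5 × 17 = 27.0.

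**2. Episodes caught by point status.** Assume episodes start evenly over Days 1–15 (in brackets, Days 1–31). Share of episodes in progress on the named day:

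| Episode length | Any of Days 4, 8, 15, 31 | Day 8 alone |
|---|---|---|
| 1 day | 20% (13%) | 7% (3%) |
| 3 days | 60% (39%) | 20% (10%) |
| 5 days | 87% (58%) | 33% (16%) |
| 7 days | 100% (71%) | 47% (23%) |

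**3. The pilot, Table 3.** ICU admission and/or invasive ventilation occurred in 6/44 over Days 1–31, but in 3/44 in the Day 8–15 window. Status on Day 8 itself could therefore show at most 3 of the 6. Non-invasive ventilation occurred in 8/44 over Days 1–31 and in 5/44 in the Day 8–15 window, so at most 5 of the 8.

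**4. *On* against *by*.** The first reads as prevalence on a day and the second as cumulative incidence. For invasive ventilation or ECMO the synopsis and Section 2.2 thus name two different quantities for one endpoint.

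**The case against.** Much of the case against is sound.

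- A reader might infer that support is measured only by durations and fixed-day status. It is not. Section 2.2 also has time to intensification of respiratory support (WHO score above 6), on a scale that scores death 10. However, that threshold excludes high-flow oxygen and NIV, which score 6, and does not register ICU admission.
- A reader might infer that episodes between visits are lost. The dates are recorded, and the duration endpoints can use them; only the percentages may leave them unused. Even that is not certain, because the sentence in Section 7.1.4 follows both the event-day list and the yes/no list. Mortality is also worded with *on Days*, although it is naturally cumulative. The pilot's ICU and NIV endpoints were worded *at Days* yet reported by window. Point status is the likelier reading, not the only one.
- A reader might worry about a falsely low Day 31 percentage. Section 8.5.3 makes that figure descriptive. The pilot had no deaths by Day 15, so it gives no sign of distortion by death at Day 8.
- Death is visible elsewhere: WHO status at Day 8 ranks it worst, the WHO categories are tabulated on all four days, and mortality is its own endpoint. That helps a careful reader but does not change what the duration endpoints measure.
- Section 8 leaves details to the SAP, which is not at hand and may say how death is handled. The silence alone is therefore no fault. The point rests on the measure the protocol itself fixes: days alive and free of support is a different endpoint from total duration.
- The Hochberg adjustment covers the primary and key secondary endpoints only, so no confirmatory claim depends on these.

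**Conclusion.** The point holds as a weakness in how secondary endpoints are defined. The two durations can make an arm with more early deaths appear to need less support. The percentages, on their likelier reading, miss episodes between the named days, and the Day 8 restriction sharpens this. The *on*/*by* conflict is plain in the text.

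A reader might go further and infer that the arm with more deaths will look better by a set amount, such as the fall from 2.21 to 1.89 days (14%) above. The documents do not support that: they give no support times for those who die, and the effect vanishes or reverses if those patients are supported as long as survivors or longer. Nor do they support saying that brief rescue episodes are typical of the second week; they say only that deterioration comes at a mean of 10 days from symptom onset. The pilot counts come from 44 patients, some with severe disease, which this trial excludes, so need here may be lower.

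The primary endpoint and the sample size are not affected.

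**What to change.** 1. Analyse days alive and free of advanced oxygen support, and days alive and free of ICU, through Day 31, scoring death by Day 31 as 0. Report deaths and raw durations in survivors beside them.
2. Define the ICU, high-flow, NIV and invasive ventilation/ECMO percentages as any use from randomisation through Days 4, 8, 15 and 31, derived from the dates recorded under Section 7.1.4, with death shown as a separate category at each day.
3. Reconcile *on* in the synopsis with *by* in Section 2.2 for invasive ventilation/ECMO, and say in Section 7.1.4 which data the percentages use.

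The cost is endpoint wording and derivation rules; no visit or data item is added. The Day 31 visit has a window of ±3 days, so the rule needs a sentence on patients last seen before Day 31. The drawback is that a support-free-days score mixes death with support, so it should not be reported without its components.

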3. INVESTIGATION PLAN

3.1. Overall Study Design and Plan Description

An overview of study design is shown in [Figure 1](#). This is a multicentre, open-label, controlled Phase 3 study in which adults requiring hospital admission and O₂ supplementation for management of moderate COVID-19 infection will be randomised in 1:1:1 to:

- Plitidepsin 1.5 mg arm: Patients will receive plitidepsin 1.5 mg/day intravenous (IV) in addition to dexamethasone on days 1 to 3 ([See Section 5. Study treatments](#)).
- Plitidepsin 2.5 mg arm: Patients will receive plitidepsin 2.5 mg/day IV in addition to dexamethasone on days 1 to 3 ([See Section 5. Study treatments](#)).
- Control arm: Patients will receive dexamethasone IV on Days 1 to 3. Additionally, in accordance with local treatment guidelines, patients in this group may receive a regulatory-approved antiviral treatment ([See Section 5. Study treatments](#)).

Randomisation will be stratified for 3 factors:

- a) Geographical Region (Europe *versus* Rest of the World);
- b) Charlson Comorbidity Index (0-1 *versus* >1) ([Appendix 11 – Age-adjusted Charlson Index](#)); and
- c) Barthel Index (≥ 90 *versus* <90) ([Appendix 7 - Barthel Index for Functional Assessment](#)).

[figure not shown]
From treatment initiation on Day 1, patients will be followed in the hospital for at least 4 days and then through Day 31 (± 3 days) or resolution/stabilisation of treatment-related adverse events, treatment-emergent adverse events of special interest, and SAEs. Patients discharged from the hospital prior to Day 8 will return to an out-patient clinic for assessments on Days 8 (± 1 day) and 31 (± 3 days). On Day 15 (± 1 day), patients will be followed up in remote or on-site visit ([Appendix 5 – Schedule of Assessments](#)).

An Independent Data Monitoring Committee (IDMC) will oversee study conduct (safety and primary endpoint), including analysis of summary safety data as per the trial requirements.

The study is expected to randomise approximately 609 patients (203 in each arm) over a period of 20 months.

Patients will be considered to be on study from the signature of the informed consent form (ICF) until the end of the follow-up period, that is, completion of the protocol-specified follow-up visit on Day 31 (± 3 days) or until resolution/stabilisation of treatment-related AEs, treatment-emergent adverse events of special interest, and SAEs that occurred through Day 31, whichever is longer.

Figure 1. Schema of the Study

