6.1.1. Allowed Medications

- Protocol-specified prophylaxis for plitidepsin infusion-related reactions.
- Protocol-specified antiemetic prophylaxis for plitidepsin.
- Supportive treatments for symptoms/AEs (e.g., antiemetics, analgesic, anti-inflammatory), including the use of locally approved agents blocking inflammatory cytokines signaling (e.g., tocilizumab, anakinra), as per local guidelines. Duration and doses of dexamethasone may be adjusted in case of clinical deterioration as per physician's judgement. Recommended medications to treat infusion-related reactions, hypersensitivity reactions, and other drug-related events are described in [Section 6.2](#).
- Standard treatments for concomitant conditions, including transfusion support, anticoagulants, insulin, and antibiotics.
- Anticoagulants (preferably low-dose low-molecular weight heparin) are allowed; as clinically indicated, appropriate monitoring of prothrombin time (PT) should be performed, if applicable. Patients who develop venous thromboembolic events during study requiring therapeutic levels of anticoagulants must be monitored closely for their platelet counts.
- SARS-CoV-2 vaccination is allowed.

Throughout the study, investigators will be allowed to administer medication for supportive treatment of symptoms and AEs, as well as standard treatments for concomitant conditions.

6.1.2. Prohibited Medications:

- Prior (within 8 weeks prior to enrolment) or concomitant administration of chloroquine phosphate or hydroxychloroquine sulfate during the study
- The use of unregistered and/or experimental medicinal products, and the off-label use of any other drug for the primary treatment of SARS-CoV-2 infection is not permitted throughout the study
- Any other concomitant antiviral treatment for COVID-19 while receiving study treatment in any of the study arms.

- Treatment with convalescent plasma or monoclonal antibodies against SARS-CoV-2 within 2 weeks before enrolment, unless objective evidence of clinical deterioration documented at least 1 week after the end of such therapy.
- Concomitant use of drugs susceptible to induce QT prolongation within 48 hours before enrolment and during the study ([Appendix 8a - Lists of Drugs That Prolong the QT Interval and/or Induce Torsades de Pointes Ventricular Arrhythmia](#)).
- Concomitant administration of treatment with strong CYP3A4 inhibitors or inducers ([Appendix 4 - Inhibitors and Inducers of CYP3A4](#)).

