15 Treatment-emergent adverse events (TEAEs): TEAEs should be documented and recorded at each visit (i.e., from initiation of study treatment on Day 1 through at least Day 31), grading severity assessed using National Cancer Institute (NCI) Common Terminology for Adverse Events (CTCAE) v5.0, and relationship to study treatment assessed by investigator judgement

16 Concomitant medications: Concomitant medications and treatments will be recorded for all patients from 28 days before the start of study treatment and through study Day 31 (± 3 days). All COVID-19 vaccinations should be recorded, regardless of when they were given, until the end of study.

17 Dexamethasone treatment: On all study arms, patients will receive dexamethasone phosphate 8 mg/day IV (equivalent to 6.6 mg dexamethasone base) on Days 1 to 3 (administered as a premedication in plitidepsin arms), following by dexamethasone phosphate 7.2 mg (equivalent to 6 mg/day dexamethasone base) PO/IV from Day 4 and up to a total cumulative dose of 60 mg of dexamethasone base (as per physician judgement according to patient clinical condition and evolution). The study allows up to a total cumulative dose of 60 mg of dexamethasone base (calculation of the total dose will also include corticosteroids administered within 72 hours before the start of the study treatment and dexamethasone administered as premedication).

18 Plitidepsin treatment: Plitidepsin 1.5 or 2.5 mg intravenous (IV) infusion for 60 minutes will be administered on Days 1 to 3. A 30 (± 5) minute window is allowed for the plitidepsin administration between each day, and plitidepsin should not be given earlier than 23.5 hours on Days 2 and 3 of previous day plitidepsin administration. No other antiviral agents to be administered during Days 1 to 3.

19 Remdesivir treatment: Consistent with local treatment guidelines, patients randomised to the control arm may receive remdesivir 200 mg IV on Day 1 followed by 100 mg/day IV on Days 2 to 5.

20 Favipiravir treatment: Consistent with local treatment guidelines, patients randomised to the control arm may receive favipiravir 1600 mg BID PO on Day 1, followed by 600 mg BID PO daily for 2 to 5 days.

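### The time-to-antiviral endpoint does not exclude the antiviral allocated to control patients, so its literal wording favours plitidepsin even with no drug effect

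*Protocol*

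**What the plan says.** The Synopsis table of objectives and endpoints sets out to compare each plitidepsin dose with "the control in terms of the need of intensification of pharmacological therapies". Section 2.2 gives two antiviral endpoints for this. One is "Time to initiation with antiviral drugs". The other is "Percentage of patients receiving subsequent antiviral drugs on Days 4, 8, 15 and 31". Only the second is limited to *subsequent* drugs.

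Section 3.1 says of the control arm that "patients in this group may receive a regulatory-approved antiviral treatment". Appendix 5, footnote 19, gives the timing for one such drug: "patients randomised to the control arm may receive remdesivir 200 mg IV on Day 1 followed by 100 mg/day IV on Days 2 to 5". The second named drug, favipiravir, also starts on Day 1 (footnote 20). Section 7.4.2.1 leaves the use of either drug to the physician, and Section 8.4 counts these antivirals as study treatment when exposure is measured.

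For the plitidepsin arms, Appendix 5, footnote 18, states: "No other antiviral agents to be administered during Days 1 to 3". Section 6.1.2 prohibits "Any other concomitant antiviral treatment for COVID-19 while receiving study treatment in any of the study arms".

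Section 7.1.4 records, by study day from Day 1, "Initiation of antivirals or immune-modulating drugs", and does not separate allocated from added drugs. A different item in that section, a yes/no question at Days 4, 8, 15 and 31, does refer to *subsequent* therapies. Section 8.5 analyses time-to-event endpoints in the ITT population, and Section 8.5.3 applies methods similar to those for the primary endpoint.

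**The concern.** The endpoint is meant to show whether patients needed more drug treatment than they were assigned. An antiviral given to a control patient on Day 1 as part of the arm is not intensification, but nothing in the endpoint or in the dated data item keeps it out of the event count. The plitidepsin arms cannot have an event in the same window without breaching the protocol.

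A programmer who follows the text would therefore build a variable that partly records the allocation itself. Analysed by log-rank and Cox methods, it could be reported as an efficacy result for plitidepsin when it shows only which arm was allowed an antiviral first.

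**Working it through.** The plan states no figure for this endpoint, so there is nothing to reproduce. The check asks how often the literal definition gives a significant result when plitidepsin does nothing.

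**Inputs from the protocol**
- 203 patients per arm (Section 8.1).
- Control antivirals start on Day 1 (Appendix 5, footnotes 19 and 20).
- No antiviral starts on Days 1 to 3 under plitidepsin (footnote 18).
- Follow-up to Day 31.
- A log-rank comparison of each dose with control (Sections 8.5.1 and 8.5.3).

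**Assumptions, because the protocol gives no figures**
- A fraction *u* of control patients starts an antiviral on Day 1; *u* runs from 0 to 80%.
- In both arms 5% or 10% of patients have a later start, spread evenly over Days 4 to 31.
- There is no true treatment effect. The log-rank test is unstratified, and deaths are not modelled.

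**Method.** Each setting has 600 simulated trials. The statistic is Z = (O − E)/√V for the plitidepsin arm, and a trial counts as favouring plitidepsin when Z < −1.96. The nominal rate in that tail is 2.5%. The Monte Carlo standard error is at most √(0.25/600) = 0.020, or 2 percentage points.

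| Control uptake *u* on Day 1 | 5% later starts | 10% later starts |
|---|---|---|
| 0% | 1.7% | 1.5% |
| 2% | 12% | 8% |
| 5% | 43% | 27% |
| 10% | 93% | 79% |
| 20% | 100% | 99.7% |
| 30% or more | 100% | 100% |

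**With the allocated antiviral left out.** When Day 1 control antivirals are not counted and later starts (10%) are equally likely in both arms, the rate is 1.8%, in line with the nominal 2.5%. The inflation therefore comes from counting the allocated antiviral.

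**What remains under that reading.** Equal later starts are themselves an assumption. A plitidepsin patient is barred on Days 1 to 3. A control patient on remdesivir is treated to Day 5, has little reason to start a second antiviral in that time, and may be barred from one by Section 6.1.2. Opportunity is unequal, and the imbalance now tends to work against plitidepsin.

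**Length of the bar.** Footnote 18 gives Days 1 to 3. Section 6.1.2 ties the bar to receipt of study treatment. If that term takes in dexamethasone, as the exposure definition in Section 8.4 does, the bar lasts longer: three days at 6.6 mg of base use 19.8 mg, and (60 − 19.8)/6 = 6.7 further days at 6 mg bring it to about Day 10 for a patient with no earlier corticosteroid. The dexamethasone row of Table 5 also runs to Day 10.

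**The case against.** The strongest reply is that the literal reading is not the natural one. The objective concerns intensification. Section 8.4 treats the control antivirals as study treatment, and Section 8.6 has a separate subgroup for control-arm antiviral use. The sibling endpoint and the yes/no item in Section 7.1.4 say *subsequent*. Together these suggest that added antivirals were meant, and the analysis plan, which is not shown, may say so. This has weight. Still, no sentence in the protocol excludes the allocated drug, and an event definition in the analysis plan cannot remove the unequal opportunity that the treatment rules create.

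Three stronger inferences are tempting but not supported:

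- **That the design fixes the result in favour of plitidepsin.** This holds only under the literal reading and with material uptake. The control antiviral is optional, and under the *subsequent* reading the bias may reverse.
- **That a simple count settles the size.** Ten control starts against none gives a two-sided Fisher p of 0.0017 at 203 per arm. That test looks only at the early window and ignores later starts. At about that uptake (10/203 = 4.9%), the log-rank comparison is significant in 27–43% of trials.
- **That footnote 18 and Section 6.1.2 plainly contradict each other.** If study treatment in Section 6.1.2 means plitidepsin, the two agree. They diverge only if dexamethasone is included. This is an ambiguity and a side issue.

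It is also fair to say that the consequence is limited. This is one of many other secondary endpoints, Section 8.5.3 opens with descriptive summaries for them, and the Hochberg procedure covers only the primary and key secondary endpoints.

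**Conclusion.** The endpoint as worded is confounded with allocation. Read literally, it gives a significant result favouring plitidepsin, with no true effect, in about 27–43% of trials at 5% control uptake, 79–93% at 10%, and close to 100% at 20% or more. These rates rest on assumed uptake and on assumed later starts of 5% or 10%. With no uptake the inflation disappears.

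If only added antivirals are counted, the direction is open and may reverse, but a between-arm test would still mix treatment effect with opportunity. Neither reading gives a comparison that can be interpreted as efficacy. The primary and key secondary conclusions are untouched, so this is a correction to make to one minor endpoint and not a threat to the trial.

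**What to change.** - Define the event as the start of an antiviral outside the allocated regimen, using *subsequent* as in the sibling endpoint and the yes/no item of Section 7.1.4, with one time origin for all arms. Have the dated item in Section 7.1.4 distinguish allocated from added drugs.
- Report both antiviral endpoints descriptively by arm, without a between-arm efficacy test.
- Base the between-arm intensification comparison on the immune-modulating endpoints. Section 6.1.1 allows cytokine-blocking agents under local guidelines without distinguishing the arms.
- If a landmark is used, set it by the longest allocated antiviral course, not by remdesivir alone. Favipiravir is given for 2 to 5 days after Day 1, and other approved antivirals follow their own product information.
- Reconcile footnote 18 with Section 6.1.2 on the period in which other antivirals are barred, so that all sites apply one rule.

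The cost is endpoint wording and one reconciled passage. No new data are needed, because exposure to allocated antivirals is already measured under Section 8.4. The loss is a between-arm p-value that could not be interpreted.
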